6.0 PRETREATMENT EVALUATION (To Be Done Day ≤ -21 ; TABLE 4)

- 6.1 Pretreatment evaluation includes complete history and physical examination.
- 6.2 Laboratory studies will include CBC with differential, blood chemistries (SMA12 including: sodium, potassium, chloride, CO_2 , BUN, creatinine, glucose, albumin, alkaline phosphatase, ALT, total protein, calcium, phosphorus, uric acid, total bilirubin, lactate dehydrogenase), serum pregnancy test for women of childbearing potential, bone marrow aspirate and biopsy with diagnostic (4-color flow cytometry to demonstrate residual disease). If bone marrow evaluation is done within 3 months of enrollment and there is no intervening treatment, this will not need to be repeated. Hepatitis B (HB) serologies will be performed including HBsAg, AHBSAG, and HBcAb. For HBcAb $^+$ (HBsAb $^{+/-}$) individuals, HB virus DNA PCR will be performed.
- 6.3 Prognostic factors will be characterized including serum β 2M; immunoglobulin heavy chain variable gene (*IGHV*) family and mutation status; leukemia cell expression of ZAP-70, CD38, and CD49d; chromosome abnormalities by FISH (13q del, +12, 11q del, and 17p del); and p53 expression. If bone marrow evaluation is done within 3 months of enrollment and there is no intervening treatment, this will not need to be repeated. In these cases, if there is any prognostic factor information missing, this can be obtained from blood. If *IGHV* mutation status and ZAP70 were previously determined at any time, they do not need to be repeated.

- 6.4 Appropriate radiological and radioisotope examinations should be performed as clinically indicated.
- 6.5 Pretreatment optional blood (20 ml) will be taken to isolate and store mononuclear cells, DNA, RNA, and plasma. Also, pretreatment optional bone marrow will be taken (5 ml) to isolate and store cells, DNA, RNA and marrow plasma. Optional blood samples will be obtained for pharmacokinetic (PK) analysis. See Table 5 for detailed schedule of optional PK analysis. Not all samples will be collected on all patients at all time points.

7.0 EVALUATION DURING STUDY

- 7.1 Monitoring will consist of biweekly (every other week ± 3 days) blood counts and SMA12 during treatment (first 8 doses of ofatumumab), then every 2 months (± 2 weeks) during maintenance, then every 3 months (± 2 weeks) during follow-up until alternative treatment for CLL/SLL or death, whichever occurs first.
- 7.2 For patients who are HBsAg $^-$, HBcAb $^+$, HBsAb $^{+/-}$, and HBV DNA $^-$ on enrollment and proceeded with treatment, HBV DNA PCR testing will be done every 2 months while on treatment and maintenance, then every 3 months during follow-up for 6 months.
- 7.3 A physician will see patients at least monthly (± 5 days) during treatment, then every 2 months (± 2 weeks) during maintenance, then every 3 months (± 2 weeks) during follow-up. A mid-level provider may evaluate patients every other week (± 3 days) during treatment (8 weeks) when not seen by the physician.
- 7.4 Patients will be seen at MDACC for mandatory visits for enrollment, ofatumumab infusions, for response assessment after 8 weekly ofatumumab doses (Month 3), during maintenance every 6 months and for follow-up at least annually. The patients' referring physician may perform other visits and laboratories in Table 4. All patients will be followed for survival.
- 7.5 A letter will be sent to the local physician outlining the patient's participation in the clinical trial and will request local physician agreement to supervise the patient's care.
- 7.6 Protocol evaluations outside MDACC will be documented by telephone, fax, or e-mail. Fax and/ or e-mail will be dated and signed by the MDACC physician, indicating that they have reviewed it.
- 7.7 Changes in schedule will be discussed with and approved by the MDACC physician investigator, or their representative prior to initiation, and will be documented in the patient record.

- 7.8 A copy of the informed consent, protocol abstract, treatment schema and evaluation during treatment will be provided to the local physician.
- 7.9 Documentation to be provided by the local physician will include drug administration records, progress notes, reports of protocol required laboratory and diagnostic studies and documentation of any hospitalizations.
- 7.10 The local physician will be requested to report to the MDACC physician investigator all life threatening events within 24 hours of documented occurrence.

The schedule of events is detailed in Tables 4 and 5. Information regarding concomitant medications will not be collected for patients on this study. This information is routinely collected and recorded as part of the patients' electronic medical record. If there is a need to refer back to this, it will be available. It is not necessary to collect and record redundant information.

Table 4. Schedule of Events

Test and Evaluations	Screening Visit Day ≤ -21	Tx W1	Tx W2	Tx W3	Tx W4	Tx W5	Tx W6	Tx W7	Tx W8	M3-24 ***	MT	End of MT	F/U
Informed consent	X												
Medical history	X												
Interval history		X*				X*							
PE with vital signs	X	X*				X*							
Serum pregnancy test	X												
Ofatumumab dose (mg)		300*	1000*	1000*	1000*	1000*	1000*	1000*	1000*	1000*	1000*	1000*	
CBC with diff, PLT	X	X*				X*							
SMA12	X	X*				X*							
Prognostic factor evaluation	X												
Bone marrow biopsy and aspiration with 4-color flow cytometry	X												
Hepatitis B (HB) surface Ag (HBsAg) and surface and core Ab (AHBSAG and HBcAb) serology													
HBsAg ⁻ , HBcAb ⁺ , HBcAb [±] , HBsAb ^{±/-} , HBV DNA ⁻ on enrollment, for HBcAb+ (HBsAb+/-) pts, HBV DNA PRC testing will be performed													
PK & PD, optional samples ***		X***	X***	X***									
Response assessment (2008 IWCLL criteria) (PE, CBC with diff, optional CT chest, abd, pelvis and BM for MRD)													
Monitoring for relapse and progression(2008 IWCLL criteria (PE, CBC with diff, and BM for MRD)													

Ag=antigen; Ab=antibody; BM=bone marrow evaluation; CBC=complete blood count; CR=complete remission; F/U=follow-up; PK=bone marrow evaluation; PE=physical examination; PD=pharmacokinetic; IWCLL=International Working Group for CLL; M=month; MT=maintenance begins on week 12 of treatment; MRD=minimal residual disease; q="every"; SMA12=sodium, potassium, chloride, CO₂, BUN, creatinine, glucose, albumin, alkaline phosphatase, ALT, total protein, calcium, phosphorus, uric acid, total bilirubin, lactate dehydrogenase; Tx=treatment; W=week; *indicates ± 3 days; **indicates ± 2 weeks; ***for detailed information about PK sample collection see Table 5, **** indicates cycle 9 begins at week 12 (M3).

Table 5. Detailed Schedule of Sampling for Optional PK Analyses

Time	Sampling time relative to ofatumumab infusion ¹
Week 1	Predose, End of Infusion (EOI), 1 h post-EOI
Week 2	Predose, EOI, 1 h post-EOI
Week 3	Predose
Week 4	Predose, EOI, 1 h post-EOI
Week 5	Predose
Week 6	-
Week 7	-
Week 8	Predose, EOI, 1 h post-EOI
Month 5	Predose, EOI, 1 h post-EOI
Month 7	Predose
Month 9	Predose
Month 11	Predose
Month 13	Predose
Month 15	Predose, EOI, 1 h post-EOI
Month 17	Predose
Month 19	Predose
Month 21	Predose
Month 23	Predose
Month 25	Predose
Month 27	Predose, EOI, 1 h post-EOI ² 1 month after last ofatumumab dose ² 3 months after last ofatumumab dose ² 6 months after last ofatumumab dose ²

EOI = end of infusion

¹ The actual date and time of each sample collection will be recorded on a pharmacokinetic sample collection form.

² Sample collected relative to last dose of ofatumumab, regardless of number of doses. Collect at any time of study day.

8.0 RESPONSE CRITERIA AND TOXICITY EVALUATION

Response assessment will be according to the 2008 International Working Group for CLL (IWCLL) guidelines¹⁵. Response will be formally assessed prior to the 9th dose of ofatumumab (prior to first bimonthly dose), then every 6 months thereafter while receiving maintenance ofatumumab and during the follow-up period (Table 4). During the follow-up phase, patients will be monitored for relapse and progression according to the 2008 IWCLL recommendations. Responses will be evaluated by physical examination, CBC, optional CT of chest, abdomen, pelvis, and bone marrow aspirate and biopsy with evaluation of residual disease (MRD) by 4-color flow cytometry.

Non-hematologic toxicity will be assessed, summarized and graded according to the Common Terminology Criteria for Adverse Events (CTCAE) Version 4.0. Hematologic toxicity will be assessed, graded, and summarized according to the

2008 IWCLL Guidelines (Table 6). Adverse events will be documented in the medical record and entered into the case report form according to the Leukemia-Specific Adverse Event Recording and Reporting Guidelines (Appendix E). PDMS/CORe will be used as the electronic case report form for this protocol. The Investigator or physician designee is responsible for verifying and providing source documentation for all adverse events and assigning the attribution for each event for all subjects enrolled on the trial.

Table 6. 2008 IWCLL Grading for Hematological Toxicity

Grade	Decrease in PLT* or HGB** (nadir) from pretreatment value, %	Absolute neutrophil count (ANC)/ μ l*** (nadir)
0	$\leq 10\%$	≥ 2000
1	11 – 24%	$\geq 1500 - < 2000$
2	25 – 49%	$\geq 1000 - < 1500$
3	50 – 74%	$\geq 500 - < 1000$
4	$\geq 75\%$	< 500

Death occurring as a result of toxicity at any level of decrease from pretreatment will be recorded as grade 5.

- * PLT counts must be below normal levels for grades 1-4. If, at any level of decrease, the PLT count is $< 20K/\mu$ l, this will be considered grade 4 toxicity, unless there was severe or life-threatening low initial PLT count ($< 20K/\mu$ l) pretreatment, in which case the patient is not evaluable for toxicity referable to PLT count.
- ** HGB levels must be below normal levels for grades 1-4. Baseline and subsequent HGB determinations must be performed before any given transfusions.
- *** If the absolute neutrophil count (ANC) reaches $<1000/\mu$ l, it should be judged to be grade 3 toxicity. If the ANC was $<1000/\mu$ l before therapy, the patient is not evaluable for toxicity referable to the ANC.

Serious Adverse Event Reporting (SAE)

A serious adverse event is – any adverse drug experience occurring at any dose that results in any of the following outcomes:

- Death
- A life-threatening adverse drug experience – any adverse experience that places the patient, in the view of the initial reporter, at immediate risk of death from the adverse experience as it occurred. It does not include an adverse experience that, had it occurred in a more severe form, might have caused death.
- Inpatient hospitalization or prolongation of existing hospitalization
- A persistent or significant disability/incapacity – a substantial disruption of a person's ability to conduct normal life functions.
- A congenital anomaly/birth defect.

Important medical events that may not result in death, be life-threatening, or require hospitalization may be considered a serious adverse drug experience when, based upon appropriate medical judgment, they may jeopardize the patient or subject and may require medical or surgical intervention to prevent one of the outcomes listed in this

definition. Examples of such medical events include allergic bronchospasm requiring intensive treatment in an emergency room or at home, blood dyscrasias or convulsions that do not result in inpatient hospitalization, or the development of drug dependency or drug abuse (21 CFR 312.32).

- Important medical events as defined above, may also be considered serious adverse events. Any important medical event can and should be reported as an SAE if deemed appropriate by the Principal Investigator or Sponsor.
- All events occurring during the conduct of a protocol and meeting the definition of a SAE must be reported to the IRB in accordance with the timeframes and procedures outlined in "University of Texas M. D. Anderson Cancer Center Institutional Review Board Policy on Reporting Serious Adverse Events". Unless stated otherwise in the protocol, all SAEs, expected or unexpected, must be reported to MDACC IND Office, regardless of attribution (within 5 working days of knowledge of the event) and GlaxoSmithKline (GSK) within 24 hours of knowledge of event.
- **All life-threatening or fatal events** with possible, probable or definite attribution to the study drug must have a written report faxed within **24 hours** (next working day) of knowledge of the event to the Safety Project Manager in the IND Office ([contact]) and to GSK within **24 hours** (next working day) of knowledge of the event. The sponsor representative should be notified by phone at [contact] to confirm receipt of the fax.
- The MDACC Internal Adverse Event Reporting Form will be used for reporting to the Sponsor (Safety Project Manager IND Office).
- Serious adverse events will be captured from the time the patient signs consent until 30 days after the last dose of drug. Serious adverse events must be followed until clinical recovery is complete and laboratory test have returned to baseline, progression of the event has stabilized, or there has been acceptable resolution of the event.
- Additionally, any serious adverse events that occur after the 30 day time period that are related to the study treatment must be reported to the IRB and the Sponsor (Safety Project Manager IND Office). This may include the development of a secondary malignancy.

Reporting to FDA:

- Serious adverse events will be forwarded to FDA by the Sponsor (Safety Project Manager IND Office) according to 21 CFR 312.32.

It is the responsibility of the PI and the research team to ensure serious adverse events are reported according to the Code of Federal Regulations, Good Clinical Practices, the protocol guidelines, the sponsor's guidelines, and Institutional Review Board policy.

9.0 REMOVAL FROM STUDY

9.1 Progressive or Relapsed Disease

Progressive disease (PD) will be characterized by at least one of the following:

- a. $\geq 50\%$ increase in the sum of the products of at least two nodes or appearance of new palpable lymph nodes on two consecutive examinations two weeks apart (at least one node must be ≥ 2 cm).
- b. $\geq 50\%$ increase in the size of liver and/or spleen as determined by measurement below the respective costal margin; appearance of palpable hepatomegaly or splenomegaly which was not previously present.
- c. $\geq 50\%$ increase in absolute number of circulating lymphocytes over baseline with $\geq 5,000$ B cells/ μ L.
- d. Transformation to a more aggressive histology (Richter syndrome) documented with biopsy.
- e. PLT or HGB decrease $\geq 50\%$ from baseline secondary to CLL/SLL.

9.2 Active HBV infection or hepatitis.

9.3 Patient request.

9.4 General or specific changes in the patient's condition render the patient unacceptable for further treatment in the judgment of the investigator

9.5 Unacceptable toxicity that in the opinion of the investigator makes it unsafe to continue therapy.

10.0 STATISTICAL CONSIDERATIONS

This is a phase II, open label, single-arm study. The primary efficacy endpoint is response rate evaluated at week12 (m3). Criteria for response will be as follows:

1. For patients enrolled in CR, patients must have pretreatment evidence of residual disease in bone marrow by MRD evaluation (4-color flow cytometry). Responders will have no evidence by evaluation of the bone marrow using the enrollment test at response assessment.
2. For patients enrolled in nPR, responders must have achieved CR by the 2008 IWCLL criteria.
3. For patients enrolled in PR, responders must have achieved either nPR or CR by 2008 IWCLL criteria.

A response rate of at least 40% with this agent will be deemed promising. 42 patients will be accrued into the study (N=21 in CR and N=21 in nPR/PR).

Simon's two-stage optimal design will be used in this study for the 2 different cohorts (CR or nPR/PR), separately. In each cohort, a sample size of 21 is chosen to differentiate between a good response rate of 40% and a poor response rate of 10% at the significance level of 0.05 with 95% power. In particular, 12 patients will be enrolled at the first stage. Enrollment will be suspended until all 12 patients have completed response assessment (m3). If there is one or fewer response, the trial will be terminated due to lack of efficacy; otherwise additional 9 patients will be treated resulting in a total of 21 patients. If there are 4 or fewer responses among 21 patients, the treatment will be concluded ineffective. The probability of early termination due to futility is 0.66.

Toxicity events for purposes of safety monitoring will be defined as ofatumumab-related grade ≥ 4 toxicity by CTCAE V.4 that persist longer than 1 week despite holding drug and or adjusting infusion rate.

The probability of toxicity will be monitored based on a beta-binomial model, assuming a priori that $p = \text{Prob}(\text{toxicity}) \sim \text{beta}(1, 1)$. The trial will be terminated if $\text{Prob}(p > .15 | \text{data}) \geq 0.9$. This rule will stop the trial if $[\# \text{ patients with toxicity}] / [\# \text{ patients evaluated}] \geq 3/7, 4/12, 5/17, 6/22, 7/27, 8/32, 9/37, \text{ or } 10/42$. The operating characteristics for toxicity are summarized in the following Table.

Table 7. Operating Characteristics Based on 1000 Simulation Study

True Prob(tox)	Pr(stop)	Median # Pts (25%, 75%)
0.05	<0.01	42 (42, 42)
0.10	0.06	42 (42, 42)
0.15	0.23	42 (42, 42)
0.20	0.47	42 (12, 42)
0.30	0.90	12 (7, 22)
0.40	>0.99	7 (7, 12)

Descriptive statistical analysis will be used to explore the data, including histograms or box-plots, proportions, means, standard deviations. The Fisher's exact test or Chi-square test will be used for the univariable analysis on categorical variables (response variable with Yes versus No, for example). The t-test or Wilcoxon test will be used for continuous variables. The Kaplan-Meier survival analysis will be performed to estimate the overall survival and time-to-progression. The log-rank test will be used to assess the difference of survival functions between two groups. Toxicity will be reported by type, frequency and severity.

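### Does calling a 40% response rate promising, and stopping the trial on one cohort's first stage, undercut the cohort-level Simon design and its 95% power?

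*Combined protocol and SAP*

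**What the plan says.** All the relevant text is in Section 10.0 of the combined protocol and SAP.

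- The general statement: "A response rate of at least 40% with this agent will be deemed promising". It does not say whether the rate is true or observed, and it gives no count.
- The unit of the design: "Simon's two-stage optimal design will be used in this study for the 2 different cohorts (CR or nPR/PR), separately".
- The error rates: "at the significance level of 0.05 with 95% power". The two rates to be told apart, with 21 patients per cohort, are 40% (good) and 10% (poor).
- The first stage: "12 patients will be enrolled at the first stage", and then "If there is one or fewer response, the trial will be terminated due to lack of efficacy". Otherwise 9 more patients are treated, for a total of 21.
- The final boundary: "If there are 4 or fewer responses among 21 patients, the treatment will be concluded ineffective".
- The early termination probability is given as 0.66, and total accrual as 42, with 21 in each cohort.

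**The concern.** Two wordings invite doubt.

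First, the only explicitly favourable statement in the section mentions 40%. As an observed rate in 21 patients that would need 9 responses (9/21 = 42.9%; 8/21 = 38.1% falls short), whereas the Simon rule rejects the 10% rate at 5 (23.8%). A cohort with 5 to 8 responses would then be neither ineffective nor promising, and the conclusion could be chosen once the data are known.

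Second, the first-stage rule ends the trial, not the cohort. The toxicity rule later in the section uses the same expression for a study-wide stop. Taken literally, futility in one cohort would close the other, and 0.66 would not be the chance that the study stops.

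The primary conclusion is at stake. If either reading were the plan's rule, the operating characteristics would differ from those stated.

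**Working it through.** **Inputs (Section 10.0).** Per cohort: first stage n1 = 12, stop at r1 = 1 or fewer; total n = 21, ineffective at r = 4 or fewer; poor rate p0 = 0.10, good rate p1 = 0.40.

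**Step 1: the plan's own figures.** Write b(x; n, p) for the binomial probability. X1 is the response count in the first 12 patients, X2 the count in the next 9.

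Early termination at p0: P(X1 ≤ 1) = 0.9^12 + 12 × 0.1 × 0.9^11 = 0.2824 + 0.3766 = 0.6590. The plan says 0.66.

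Probability of rejecting the poor rate: the sum over x1 = 2 to 12 of b(x1; 12, p) × P(X2 ≥ 5 − x1; 9, p).

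| x1 | p = 0.10 | p = 0.40 |
|---|---|---|
| 2 | 0.2301 × 0.0530 = 0.0122 | 0.0639 × 0.7682 = 0.0490 |
| 3 | 0.0852 × 0.2252 = 0.0192 | 0.1419 × 0.9295 = 0.1319 |
| 4 | 0.0213 × 0.6126 = 0.0131 | 0.2128 × 0.9899 = 0.2107 |
| 5 or more | 0.0043 × 1 = 0.0043 | 0.5618 × 1 = 0.5618 |
| Sum, from unrounded terms | 0.0488 | 0.9535 |

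Type I error is 0.0488 (stated level 0.05) and power 0.9535 (stated 95%). A search over two-stage designs with n up to 32 for these rates, level and power returns 1/12 and 4/21 as the optimal design. Its expected size at p0 is 12 + (1 − 0.659) × 9 = 15.1 patients. Everything stated reproduces, and it does so with success at 5 or more of 21 in a single cohort.

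**Step 2: what the 40% is.** The paragraph after the promising-rate sentence uses the same 40% as the good rate, set against a poor rate of 10%. That makes it the alternative, a true rate. The critical proportion, 5/21 = 23.8%, lies between 10% and 40%, as it must if both error rates are to be small. If 9 responses were required after passing the first stage, the chance of success at a true 40% would be 0.476 and the type I error about 0.0001. Neither resembles the stated 95% and 0.05. The plan's own figures therefore rule out the observed-rate reading.

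**Step 3: what the trial means in the first-stage rule.** These elements stand side by side:

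- The paragraph opens by applying the design to the two cohorts separately, and its next sentence concerns each cohort.
- The stopping sentence ends with 9 more patients and a total of 21. That is a cohort; the study has 42.
- The toxicity boundaries run to 10/42, so that rule is marked as study-wide by its denominators.
- The 0.66 equals P(X1 ≤ 1) in 12 patients at 10%, a single-cohort figure. With both cohorts at 10%, the chance that at least one stops is 1 − (1 − 0.659)² = 0.884, which is not what the plan gives.

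**Step 4: the literal whole-trial reading, for scale.** At a true 40%, P(X1 ≤ 1) = 0.0196. If failure in either cohort's first stage closed both, a cohort's power with both true rates at 40% would be 0.9535 × (1 − 0.0196) = 0.935, under 2 points below 0.9535. If the other cohort's true rate were 10%, and its failure took effect before this cohort finished, power would be 0.9535 × (1 − 0.659) = 0.325. The large loss thus needs both a reading the context does not support and one inactive cohort.

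**The case for a change.** The strongest case is that the plan never states the favourable conclusion as a count. It defines failure as 4 or fewer of 21 and leaves success to be inferred, while the one favourable sentence is phrased as a verdict and cites 40%. The zone in between is not remote: at a true rate of 40%, a cohort passes the first stage and ends with 5 to 8 responses with probability 0.9535 − 0.4762 = 0.477, about as often as it reaches 9 or more (0.476). In a single-arm, open-label study, a rule open to two readings could be settled after the fact. Likewise, one expression about terminating the trial serves both a cohort rule and a study-wide toxicity rule. The cohorts have different endpoints (clearance of residual disease against an improved response category), so their true rates may well differ.

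The remarks on drafting stand. It would be clearer to state that 5 or more of 21 rejects the 10% rate, to write cohort in the first-stage rule, and to label 0.66 as per cohort at a true 10%. The inference from drafting to a defect does not stand. Failure is fixed in advance at 4 or fewer, the test is of 10% against 40%, and the complement of the boundary is rejection of 10%. No count of 9 appears anywhere in the plan. Any analyst applying the design would make these clarifications as a matter of course, and they alter no figure.

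**Conclusion.** The concern does not hold. The 40% and the 5-of-21 boundary are different quantities, the design alternative and the critical value, and they fit together as in any Simon design. The first-stage rule reads in context as a cohort rule. On that reading type I error is 0.0488, power 0.9535 and early termination probability 0.659 at a true 10%, in agreement with the stated 0.05, 95% and 0.66.

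The figures 0.476 and 0.325 are correct arithmetic for rules the plan does not state: an observed rate of at least 40%, and closure of both cohorts when one fails. The conclusion assumes that the cohorts are run and judged separately, as Section 10.0 says, and that the 40% carries the same meaning in adjacent paragraphs. What is left is an optional tidying of wording.

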- Chronic obstructive pulmonary disease, moderate to severe (unapproved use); risk of grade 3 bronchospasm during infusion.
- Cytopenias, including prolonged severe neutropenia and thrombocytopenia may occur; monitoring recommended.
- Hepatitis B infection, carriers or at risk of infection; risk of hepatitis B reactivation with fulminant hepatitis, hepatic failure, and death; evaluate for evidence of infection before beginning treatment and closely monitor for reactivation for 6 to 12 months following therapy; discontinue therapy if viral hepatitis occurs.
- Infusion reactions, some serious (eg. bronchospasm, dyspnea, laryngeal edema, pulmonary edema, angioedema, cardiac ischemia/infarction) have been reported; especially during first 2 infusions; premedication is recommended; depending on the severity of the reaction, adjustment in infusion rate, interruption, and/or discontinuation of therapy is recommended.
- Obstruction of small intestinal may occur.
- Progressive multifocal leukoencephalopathy (PML) including fatalities, may occur; new onset or changes in preexisting neurological signs and symptoms may be indicative of PML; discontinue therapy if PML occurs.
- Viral vaccination, live; do not use in patients who recently received ofatumumab therapy.

Potential Side Effects:

Common

- Dermatologic: rash (all grades, 14% to 17%; grade 3 or greater, less than 1% to 2%)
- Gastrointestinal: diarrhea (18% to 19%), nausea (11% to 12%)
- Hematologic: anemia (all grades, 16% to 17%; grade 3 or greater, 5% to 8%)
- Respiratory: bronchitis (all grades, 11% to 19%; grade 3 or greater, less than 1% to 2%), cough (19%), dyspnea (all grades, 14% to 19%; grade 3 or greater, 2% to 5%), pneumonia (all grades, 23% to 25%; grade 3 or greater, 14% to 15%), upper respiratory infection (3% to 11%)
- Other: fatigue (15%), Fever (all grades, 20% to 25%; grade 3 or greater, 3% to 5%)

Serious

- Gastrointestinal: bowel obstruction
- Hematologic: neutropenia, Grade 3 or greater (42%)
- Hepatic: relapsing type B viral hepatitis
- Immunologic: infectious disease (all grades, 70%; grade 3 or greater, 29%), sepsis (all grades, 8% to 10%; grade 3 or greater, 8% to 10%)
- Neurologic: progressive multifocal leukoencephalopathy
- Other: complication of infusion (first infusion, 44%; second infusion, 29%)

Unused and Expired Study Drug:

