5.0 TREATMENT PLAN

This is a single-arm, open label trial of ofatumumab. Treatment with ofatumumab will be 300 mg dose 1, then 1,000 mg weekly x 7 (referred to as "treatment"), then 1,000 mg every 2 months beginning on week 12 for a total of 2 years of treatment or until progression (referred to as "maintenance"). The "follow-up" period will be the period after completion of "maintenance".

Ofatumumab pre-medication must be given within 30 minutes to 2 hours prior to each infusion:

Table 1. Recommended Pre-medication Prior to Ofatumumab Infusions

Infusion #	Acetaminophen (po) or equivalent	Antihistamine (iv or po) diphenhydramine or equivalent	Glucocorticoid (iv) prednisolone or equivalent
1 st	1000 mg	50 mg	50 mg
2 nd	1000 mg	50 mg	50 mg
3 rd -N th	1000 mg	50 mg	0 – 50 mg ¹

1. If the 2nd infusion was completed without the patient experiencing any grade 3 AE, pre-medication with corticosteroid may be reduced or omitted before the 3rd to Nth infusion at the discretion of the investigator.

First Infusion of 300 mg and 1000 mg Ofatumumab

The first dose administered of ofatumumab should be 300 mg to minimize infusion reactions. The initial rate of the **300 mg** (0.3 mg/ml) and first **1000 mg** (1.0 mg/ml) ofatumumab doses should be 12mL/hr. If no infusion reactions occur the infusion rate should be increased every 30 minutes according to Table 2, to a maximum of 200 mL/hr.

Table 2. Infusion Rate at 1st and 2nd Ofatumumab Infusion

Time	mL/hour
0 – 30 minutes	12
31 – 60 minutes	25
61 – 90 minutes	50
91 – 120 minutes	100
121 – 150 + minutes	200

If an infusion reaction develops, the infusion should be temporarily slowed or interrupted. Additional corticosteroids may be given at the discretion of the treating physician. Upon restarting, the infusion rate should be half of the infusion rate at the time the infusion was paused. If, however, the infusion rate was 12 mL/hour before the pause, the infusion should be restarted at 12 mL/hour. Hereafter, the infusion rate may be increased according to the judgment of the investigator, in the manner described in this section.

Subsequent Infusions of 1000 mg Ofatumumab

If the previous infusion was completed without any grade ≥ 3 infusion-associated AE, the subsequent infusion of ofatumumab 1000mg (1.0mg/mL) can start at a rate of 25 mL/hour and should be doubled every 30 minutes up to a maximum of 400 mL/hr, according to

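### Is the Section 10 toxicity stopping rule unworkable because it names no observation period and no enrollment pause at its looks?

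*Combined protocol and SAP*

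**What the plan says.** Section 10.0 defines the monitored event by attribution, grade and persistence: "Toxicity events for purposes of safety monitoring will be defined as ofatumumab-related grade" 4 or worse under CTCAE version 4, lasting more than a week despite holding drug or adjusting the infusion rate. Both cohorts are pooled. The trial stops if the posterior probability that toxicity exceeds 15% reaches 0.9 under a beta(1,1) prior. The boundaries, "3/7, 4/12, 5/17, 6/22, 7/27, 8/32, 9/37" and finally 10/42, are counts over "patients evaluated". Table 7 gives stopping probabilities and the median and quartiles of a column headed # Pts.

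Three other provisions bear on timing, and none is linked to this rule:

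- Section 5.0 gives eight weekly doses, "then 1,000 mg every 2 months beginning on week 12 for a total of 2 years of treatment or until progression". Section 8.0 adds: "Response will be formally assessed prior to the 9th dose of ofatumumab".
- The one enrollment pause in Section 10.0 serves the efficacy rule, separately in each cohort: "Enrollment will be suspended until all 12 patients have completed response assessment (m3").
- Section 8.0 sets a reporting period: "Serious adverse events will be captured from the time the patient signs consent until 30 days after the last dose of drug".

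**The concern.** A rule that monitors one toxicity probability per patient normally states the window for that probability. Here the week-12 visit is named for response and the 30-day post-treatment limit for serious event reporting, but neither is named for the stopping rule. Dosing at months 3, 5, ..., 23 gives 11 infusions after the first 8, so 11 of 19 follow the first response assessment. A 15% limit by week 12 is a different standard from 15% over two years.

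The second worry is exposure. The patient numbers in Table 7 assume complete outcomes at each look. If enrollment continues while patients are observed, more will have been treated than the table shows. This is the only stated trial-level toxicity stop; removal of individuals under Section 9.5 and serious event reporting do not replace it. The drug information in Section 3.0 also foresees late harm, asking sites to "closely monitor for reactivation for 6 to 12 months following therapy" for hepatitis B. If the rule missed maintenance toxicity, or acted only after everyone was enrolled, its protection would be weaker than Table 7 suggests.

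**Working it through.** **1. Boundaries.** Inputs from Section 10.0: beta(1,1) prior, limit 0.15, cut-off 0.9. With x events in n patients the posterior is Beta(1+x, 1+n−x), and P(p > 0.15) = P(Bin(n+1, 0.15) ≤ x).

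- n = 7: x = 3 gives P(Bin(8, 0.15) ≤ 3) = 0.979; x = 2 gives 0.895. The boundary is 3.
- n = 42: x = 10 gives P(Bin(43, 0.15) ≤ 10) = 0.951; x = 9 gives 0.899. The boundary is 10.
- The six looks between reproduce in the same way.

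**2. Table 7.** Exact binomial recursion over looks at 7, 12, ..., 42, each with complete outcomes:

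| True toxicity | Exact Pr(stop) | Table 7 |
|---|---|---|
| 0.05 | 0.006 | <0.01 |
| 0.10 | 0.060 | 0.06 |
| 0.15 | 0.229 | 0.23 |
| 0.20 | 0.501 | 0.47 |
| 0.30 | 0.912 | 0.90 |
| 0.40 | 0.995 | >0.99 |

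The 0.20 row differs by 0.031. One simulation standard error is √(0.5 × 0.5 / 1000) = 0.016, so this is about two standard errors. At 30% the cumulative stopping probability is 0.353 by 7 patients, 0.546 by 12, 0.670 by 17 and 0.755 by 22, which gives 12 (7, 22) as printed. The table is therefore right for patients evaluated, the rule's own denominator.

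**3. If only events by week 12 counted.** The monitored rate is the two-year rate times the share occurring by week 12. The documents do not give that share, so 25/50/75/100% is assumed. For example, 0.30 × 0.50 = 0.15, and the 0.15 row gives 0.229.

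| Two-year rate | 25% | 50% | 75% | 100% |
|---|---|---|---|---|
| 0.20 | 0.01 | 0.06 | 0.23 | 0.50 |
| 0.30 | 0.02 | 0.23 | 0.64 | 0.91 |
| 0.40 | 0.06 | 0.50 | 0.91 | >0.99 |

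This moves the reader to another row of Table 7. The drop arises only if maintenance events are excluded, and no sentence in Section 10.0 excludes them.

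**4. If events count when they occur.** The event count among the first n enrolled patients can only rise. A boundary that would be crossed at complete follow-up is crossed at the deciding event, at that time or sooner. Pr(stop) for a given two-year rate stays as in Table 7; only the date of stopping moves.

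**5. Enrollment when the rule acts.** The documents give no accrual rate. Assumptions: regular accrual, cohorts filling evenly, both cohorts continuing, and the efficacy pause at 24 pooled patients until the 24th reaches month 3.

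Waiting for complete follow-up, at 1 patient per month the 7th enters at month 6. A two-year period ends at month 30. The 24th enters at month 23 and the 25th at month 26, so 28 are enrolled before month 30. With a 12-week period, 9 are enrolled before month 9. Medians (quartiles) enrolled at 30% toxicity:

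| Accrual per month | 12 weeks, waiting | Two years, waiting | Two years, stop at deciding event, even timing |
|---|---|---|---|
| 1 | 14 (9, 24) | 33 (28, 42) | about 24 to 26 (21, 36 to 37) |
| 2 | 17 (12, 24) | 42 (42, 42) | about 39 (30, 42) |

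With earlier events (mean 6 months) the last column becomes about 19 (13, 29) and 24 (18, 38). At 4 per month the 24th enters at month 5.75, the 25th at 8.75 and the 42nd at 8.75 + 17 × 0.25 = 13.0. Everyone is then enrolled by month 13, so no rule could limit enrollment on account of events later than that.

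**6. What pauses would cost.** There are seven looks before full enrollment. Pausing at each could add up to 7 × 3 = 21 months with a 12-week period, or 7 × 24 = 168 months with two years.

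**7. The hepatitis B example.** Reactivation 6 to 12 months after therapy lies beyond week 12 and beyond 30 days after the last dose, so it does not separate the two candidate periods. It is also handled elsewhere: exclusion in Section 4.2, PCR testing in Section 7.2 and removal in Section 9.2.

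**The case for a change.** The strongest case is that two competent teams could apply the rule differently. One might close each patient's toxicity record at the month-3 visit, by analogy with the response endpoint; the other might keep it open through maintenance. If half of all toxicity came after week 12, a true 30% two-year rate would stop the trial with probability 0.23 under the first practice and 0.91 under the second. A few sentences in Section 10.0 would remove the doubt, and the existing pause is per cohort, for response, and not aligned with the pooled looks.

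Part of this stands. The text is silent on the period, and with fast accrual and late events enrollment would be complete before the rule could act. But the first practice adds a cut-off that Section 10.0 does not contain. Serious events are captured throughout dosing, and related life-threatening or fatal ones must be reported within 24 hours, so the information needed to count events as they occur is available. Late toxicity under fast accrual is a limit of any such rule: naming a period would not cure it, and pausing at every look would be very slow. Nor does Table 7 have to mean patients treated, since the rule counts patients evaluated. With slow accrual the two are close anyway: 8 enrolled when 7 are evaluated, at 0.5 per month and a 12-week period.

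**Conclusion.** This is a gap in wording that those running the monitoring can fill sensibly: count each qualifying related event when it occurs, maintenance included, against the listed boundaries, and read # Pts in Table 7 as patients evaluated. On that reading the eight boundaries are exact, the stopping probabilities hold for the two-year rate (0.501, 0.912 and 0.995 at 20%, 30% and 40%), and the sample size is untouched. The loss of stopping probability appears only if maintenance events are excluded and an assumed share of toxicity comes late. The largest exposure figures need fast accrual, or a two-year wait even after the boundary is certain to be crossed. Neither the accrual rate nor the event timing is in the documents, so these figures are illustrations on assumed inputs. The absence of pauses at the toxicity looks is a fair trade-off against up to 21 or 168 added months. No change to the plan follows.
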